#### Secondary and exploratory analysis.

We will test the following three secondary hypotheses: subjects who received Naloxegol 25 mg given once in the morning every day will have (1) fewer opioid-related side effects, (2) less need of indwelling catheterization determined by the residual volume to be above 400 ml, and (3) improved quality of recovery as compared to placebo.

The two groups will be compared on the incidence of any opioid-related side effects using a logistic regression. The frequency, severity, and bothersomeness for each of the 12 opioid-related side effects on POD 1 and 2 will be summarized. We will compare the two groups on incidence (any versus none) of need for indwelling urinary catheterization (defined as residual urine volume > 400 ml) using logistic regression. The two groups will also be compared on the Quality of Recovery scale measured on POD 2 (or day of discharge if it occurs earlier) using a linear mixed model with an autoregressive correlation structure. All the analyses will be adjusted for imbalanced baseline characteristics, if any. The hypothesis-wise 2-sided type I error for each of the secondary outcome will be controlled at 0.017 (i.e., 0.05/3, Bonferroni correction).

In addition, we will summarize the following exploratory outcomes, including satisfactory of the quality of recovery (a subjective 100-point scale) and length of hospital stay after surgery.

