#### **B.** Secondary Aims

#### Secondary Aim 1:

To evaluate the effect of Naloxegol on other opioid related side effects.

*Hypothesis.* Patients in Naloxegol group have fewer opioid-related side effects than control group. We will use a validated composite outcome, Opioid–Related Symptom Distress Scale (ORSDS), to evaluate opioid-related side effect. ORSDS is 4-point scale that evaluates 3 symptom distress dimensions (frequency, severity, bothersomeness) for 12 opioid related side

effects [53]. ORSDS questionnaire will be administered by a trained research fellow on first, second, and third postoperative mornings while patients remain hospitalized.

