#### 2. STUDY DESIGN and METHODS

#### A. Study Overview

We propose to assess the effect of Naloxegol on reversing opioid-related side effects in patients recovering from elective primary hip surgery under spinal anesthesia who will be randomly assigned to oral Naloxegol or placebo for two postoperative days or until the date of discharge, whichever occurs earlier (**Table 1**). The design will be a randomized, double-blind, placebo-controlled trial of oral Naloxegol in adults having elective primary hip or knee surgery under spinal anesthesia. The study will be performed at the Cleveland Clinic hospitals.

	Preopera tive visit	Morning of surgery	During surgery	PACU*	POD** 1	POD 2	Day of discharge	
Screening for eligibility	Х	Х						
Consenting	Х							
Baseline medical, demographics, Apfel score, Patient functionality and drug history	Х	х						
Pertinent blood studies (laboratory)	Х				Х	х		
AE/SAE collection		Х			Х	Х		
Study drug (in morning, 1 hr before or 2 hr after meal)		Х			х	х		
Bladder scan at least 2 hours after study drug (morning)					х	Х		
Bladder scan (evening)				Х	х	Х		
Intraoperative record data collection			Х					
Opioid–Related Symptom Distress Scale (ORSDS)					х	х	Х	
Opioid complications survey***				X	х	Х	х	
Numerical pain score				Х	Х	Х	Х	Х
Quality of recovery survey							Х	

Table 1: study flowchart.(Detailed information will be in the CRF's)

\* PACU = post-anesthesia care unit

\*\* POD = post-operative day

\*\*\* Opioid complications survey includes nausea, vomiting, itching, ileus, anti-emetic use, antipruritic use, anti-opioid use

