#### F. Measurements

Data will be recorded on a case report form (CRF) which will be available electronically and on paper format.

Demographic data to be obtained includes height (cm), weight (kg), age (yr), gender, physical status (ASA), and self-declared ethnicity. Patients will be questioned for social history (tobacco) and medical history (pulmonary disease, kidney disease, diabetes mellitus, neurological disease, chronic pain conditions, illegal drug usage, alcohol abuse, myocardial infarction, previous surgery or stent placement and medications usage). Available preoperative laboratory tests and medication list will be recorded. Individual risk for nausea and vomiting will be determined using the Apfel score.

Data obtained from electronic medical records will include: operation time, surgery type, intraoperative opioid consumption, postoperative opioid consumption in PACU and in ward,

breakthrough pain medication requirements, pain scores in PACU and ward, requirement of oxygen in PACU and ward, nausea and vomiting, requirement of antiemetics, pruritus, requirement of antihistaminic medications, ambulation time, flatus, ileus, bowel movements, constipation, length of stay and any side effects or complications. Preoperative and postoperative laboratory data including but not limited to liver function and coagulations test results will also be collected from electronic medical records. Patient functionality will also be recorded including bathing, toileting, walking and moving.

The Residual volume will be measured within 30 minutes after urination using the batterypowered, portable Bladder scan™ BVI 3000® (Verathon, Bothell, WA, USA). The scanner will be placed on the suprapubic area and held stationary during measurement scanning. The diameter of the bladder and volume of urine will be calculated from the scan data. Scans will be repeated several times to ensure accuracy in measurements. The average of the measurements at each measurement time will be analyzed. All clinical procedures will be performed by trained MD research fellows in the ward twice daily. Surgical team will be blinded to volume determined by scanning and we will also record if they had ordered indwelling catheterization.

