We will use Myles QoR scale to formally evaluate quality of recovery on 2 or day of discharge (whichever comes earlier). Myles QoR scale is a validated scoring system allows quantification of patient's early postoperative health status, which is also a description of quality of recovery[32]

ORSDS is 4-point scale that evaluates 3 symptom distress dimensions (frequency, severity, bothersomeness for 12 opioid related side effects[53]. ORSDS questionnaire will be administered by a trained research fellow on first and second postoperative days/day of discharge (whichever comes earlier)

Patient satisfaction with their recovery will be questioned before discharge using a 0-100 scale (where 0 indicates no satisfaction and 100 indicates complete satisfaction).

Adverse events and serious adverse events occurring at any time during the study period will be recorded on a specific form in the CRF.

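### The graded ORSDS composite named for Secondary Aim 1 is never compared between arms; the only planned test is on the incidence of any side effect

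*Combined protocol and SAP*

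**What the plan says.** Secondary Aim 1 (Study Objectives, section B) states the hypothesis as "Patients in Naloxegol group have fewer opioid-related side effects than control group". For the outcome it says "We will use a validated composite outcome" and names the ORSDS, which rates 12 symptoms on how often they occur, how severe they are and how bothersome they are.

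Section G, under Secondary and exploratory analysis, restates the hypothesis and gives one comparison: "The two groups will be compared on the incidence of any opioid-related side effects using a logistic regression". The next sentence covers the graded data: "The frequency, severity, and bothersomeness for each of the 12 opioid-related side effects on POD 1 and 2 will be summarized". Each of the three secondary hypotheses is tested at two-sided 0.017 (0.05/3).

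Section F covers how the questionnaire is given but not how it is scored. The appendix reproduces the item grid, including a column for symptoms not experienced. No section defines an ORSDS total, a symptom count or a scoring formula, and none plans to compare one between arms.

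The schedule is stated in two ways. Secondary Aim 1 has the questionnaire given "on first, second, and third postoperative mornings while patients remain hospitalized". Section F has it given "on first and second postoperative days/day of discharge (whichever comes earlier", and section G summarises POD 1 and 2.

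**The concern.** The aim is about the burden of side effects, measured on a graded multi-symptom scale. The test asks something narrower: whether fewer patients report any symptom at all. A patient who goes from eight severe symptoms to one mild one counts as positive both times. The 12 items include dry mouth, fatigue and drowsiness, so a large share of patients in both arms may report at least one.

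Two things are at stake. First, a null result could mean that nearly everyone had some symptom, and would say little about whether naloxegol reduced their number or intensity. Second, if the team later compared an ORSDS score, that comparison would be post hoc, although the protocol names the scale as the outcome. This concerns one of three alpha-controlled secondary hypotheses.

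**Working it through.** **1. The text side by side.**

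| Element | Secondary Aim 1 | Section G |
|---|---|---|
| Hypothesis | Fewer side effects | Fewer side effects |
| Outcome | ORSDS composite, 12 graded symptoms | Incidence of any side effect (binary) |
| Use of grades | Part of the named outcome | Summarised by item, not tested |

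The appendix form codes frequency and severity from 1 to 4. It codes the five bothersomeness levels from 0.8 to 4.0, so all three dimensions share a maximum of 4. That coding suggests the dimensions are meant to be combined into a score. This is an inference, because the combining rule is not given.

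**2. The plan's own sample size.** Section H assumes an effect size of 0.4, four measurements, correlation 0.3, 90% power and two-sided alpha 0.05. Then n = 2 × (1.960 + 1.282)² × [(1 + 3 × 0.3)/4] / 0.4² = 62.4, which agrees with the stated 62 (power at 62 is 89.8%). This figure belongs to the primary outcome. It is used below only as the number per arm.

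**3. Do the documents show a ceiling?** No ORSDS rates are given. The Introduction gives nausea and vomiting 20-70%, pruritus up to 50% and urinary retention 5-70%. If these were independent, the chance of at least one would be:
- Low end, pruritus near 0: 1 − 0.80 × 1 × 0.95 = 24%
- Low end, pruritus 50%: 1 − 0.80 × 0.50 × 0.95 = 62%
- High end: 1 − 0.30 × 0.50 × 0.30 = 95.5%

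The other eight symptoms on the form can only raise these. A ceiling is therefore possible but not established. At 62 per arm and two-sided 0.05/3, 80% power needs a fall from 62% to 33%, or from 95.5% to 76%.

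**4. A case that can be checked by hand (assumed rates).** Take 12 independent symptoms at 30% each, a 25% relative cut in every one, a single day, 62 per arm and critical value 2.394.
- Any versus none: control 1 − 0.70¹² = 98.6%; treated 1 − 0.775¹² = 95.3%. Power = Φ[(0.0331 − 2.394 × 0.0308)/0.0307] ≈ Φ(−1.3) ≈ 9%.
- Count: means 3.6 and 2.7; summed variance 12 × 0.3 × 0.7 + 12 × 0.225 × 0.775 = 4.61; standard error √(4.61/62) = 0.273. Power = Φ(0.9/0.273 − 2.394) ≈ 82%.

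With latent correlation 0.3 between symptoms, the same cut gives 87.8% against 79.8% for any versus none (power 12%), and power 32% for the count. At symptom rates of 5-10%, power is low for both: 5-13% and 6-25%.

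**5. Two-day simulation (assumed rates).** Item rates 10-40%, latent correlation 0.1-0.5, a 30% cut in all 12 items, 62 per arm, two-sided 0.05/3. Any versus none uses a two-proportion test over both days. The count and graded score use a mixed model with group and day. The graded score is a stand-in, not taken from the documents: the mean of the three dimensions, zero if the symptom is absent, averaged over 12 items.

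| Item rate, correlation | Any/none | Count | Graded |
|---|---|---|---|
| 30%, 0.3 | about 13% | about 51% | about 50% |
| 40%, 0.1 | 0% | about 96% | about 95% |
| 10%, 0.5 | about 10% | about 10% | about 10% |
| All 12 combinations | 0-16% | 10-96% | 10-95% |

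If only 4 of the 12 items respond, power is 0-3% for any versus none and 2-15% for the count or graded score.

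**The case against.** **The mismatch may be one of vocabulary.** A composite outcome often means any of its components, and fewer side effects can mean a lower incidence. That is a fair reading of the hypothesis alone. It fits less well with an aim that goes on to describe three graded dimensions, or with the form's common maximum of 4.

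**A reader might infer that the endpoint is undefined.** Two other sources of side-effect data exist. The Table 1 footnote reads "Opioid complications survey includes nausea, vomiting, itching, ileus, anti-emetic use, antipruritic use, anti-opioid use", and section F takes from the medical record "flatus, ileus, bowel movements, constipation, length of stay and any side effects or complications". The documents do not support that stronger reading. Secondary Aim 1 ties opioid-related side effects to the ORSDS, the sentence after the test refers to the 12 side effects on POD 1 and 2, and the form has a column for symptoms not experienced. The other two sources are not linked to this aim. Any of the 12 items on POD 1-2 is the natural reading, and one line in the SAP would settle it.

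**A reader might also infer that the test is bound to fail at a ceiling.** That is not shown. The item rates and correlations above are assumptions, and the documents' background ranges run from 24% to 95.5%. The retention range may overstate the position here, because conditions that cause retention are excluded.

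**The power gain assumes an effect on every symptom.** Introduction C describes naloxegol as acting mainly at peripheral receptors, while the form includes drowsiness, confusion and difficulty concentrating. This objection stands. If few symptoms respond, every all-item summary is weak, though any versus none is no better.

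**The scoring rule is not in the documents.** This also stands. The graded-score power describes a constructed score, and the validated one may behave differently.

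**Conclusion.** The mismatch holds on the text alone: Secondary Aim 1 names a graded composite, and the plan followed as written never compares it between arms. The any-of-12 endpoint is valid but answers a narrower question, because it ignores the number and grade of symptoms.

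The size of the loss cannot be fixed from the documents. Over the uniform-effect scenarios examined, a count or graded score did about as well as any versus none or much better. In the middle case power was about 50% against about 13%. With rare, highly correlated symptoms there was no gain. These figures rest on assumed item rates, assumed correlations and a uniform 30% cut. The textual point does not depend on them.

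The primary analysis, alpha control and data collection are not affected, and no inflation of type I error is implied. Nor are the graded data discarded: they are reported, but not tested. The change is worth making because it is cheap and removes a gap between aim and test.

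**What to change.** Before unblinding, amend section G so that the ORSDS composite score is the single tested outcome for secondary hypothesis 1, at the existing 0.05/3 level. Score it by the rule of the instrument the protocol cites, and write that formula into the SAP. Compare arms over POD 1 and 2 with a linear mixed model containing group, day and within-patient correlation, using every assessment available, including those from patients discharged early. Section G already uses mixed models. In null simulations this one held its level: 1.4-2.1% with complete data, and 1.4-2.0% when 20% of one arm and 40% of the other had POD 1 only (nominal 1.67%).

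Report the 0-12 symptom count as supportive. Report the proportion with any of the 12 ORSDS items on POD 1-2 as descriptive, defined in those terms. If the scoring rule cannot be fixed before unblinding, test the count instead; it needs no scoring rule but drops grade.

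The cost is SAP wording, since the form is already being completed. The result becomes a mean difference rather than an odds ratio, and an all-item summary dilutes an effect confined to a few symptoms.

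As a separate editorial point, reconcile the three-morning ORSDS schedule in Secondary Aim 1 with the two days in sections F and G.

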## Appendix

# Opioid-Related Symptom Distress Scale (ORSDS) [53]

In the	Didnot	lf yes	s, how freque	antly did it d	occur?		If yes, how	v severe?		And how bothersome was the experience?							
last 24 h, have you experience any of the following?	experience	Rarely	Occasionally	F requently	Almost constantly	Slightly	Mo der ately	Severe	Very	Not at all	A little bit	Some what	Quite a bit	Very much			
Nausea		1	2	3	4	1	2	3	4	0.8	1.6	2.4	3.2	4.0			
Vomitina		1	2	3	4	1	2	3	4	0.8	1.6	2.4	3.2	4.0			
Constipation	ı	1	2	3	4	1	2	3	4	0.8	1.6	2.4	3.2	4.0			
Difficulty passing urine		1	2	3	4	1	2	3	4	0.8	1.6	2.4	3.2	4.0			
Difficulty concentratin	ig	1	2	3	4	1	2	3	4	0.8	1.6	2.4	3.2	4.0			
Drowsiness/ difficulty staying awake		1	2	3	4	1	2	3	4	0.8	1.6	2.4	3.2	4.0			
Feeling lightheaded or dizzy		1	2	3	4	1	2	3	4	0.8	1.6	2.4	3.2	4.0			
Feeling confused		1	2	3	4	1	2	3	4	0.8	1.6	2.4	3.2	4.0			
Feelings ofgeneral fatigue or weakness		1	2	3	4	1	2	3	4	0.8	1.6	2.4	3.2	4.0			
Itchiness		1	2	3	4	1	2	3	4	0.8	1.6	2.4	3.2	4.0			
Dry mouth		1	2	3	4	1	2	3	4	0.8	1.6	24	32	4 0			
Headache		1	2	3	4	1	2	3	4	0.8	1.6	24	32	4.0			

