#### QoR-15 Patient Survey

Date:	/	_/
Preope	rative	

Study #: \_\_\_\_\_

Postoperative

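### QoR-15 is tested on a single postoperative value with no preoperative score to adjust for, which gives up precision that could be had cheaply

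*Combined protocol and SAP*

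**What the plan says.** Every place that schedules the two questionnaires puts them after surgery.

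- **Timing of QoR-15** (2.F Measurements): "We will use Myles QoR scale to formally evaluate quality of recovery on 2 or day of discharge (whichever comes earlier". Secondary Aim 3 gives the same timing.
- **Timing of ORSDS** (2.F Measurements): "ORSDS questionnaire will be administered by a trained research fellow on first and second postoperative days/day of discharge (whichever comes earlier". Secondary Aim 1 names three postoperative mornings instead of two, but no preoperative one.
- **Baseline collection** (2.A Study Overview, Table 1): the row reads "Baseline medical, demographics, Apfel score, Patient functionality and drug history". Neither questionnaire is in it, and Table 1 marks both only on postoperative days or at discharge.
- **Analysis of QoR-15** (2.G, Secondary and exploratory analysis): the groups are compared on the "Quality of Recovery scale measured on POD 2 (or day of discharge if it occurs earlier". The significance level is 0.05/3, given as 0.017. Covariates enter only if they are imbalanced at baseline, which 2.G defines as a standardised difference above 0.2.
- **Analysis of side effects** (same section): "The two groups will be compared on the incidence of any opioid-related side effects using a logistic regression".
- **Primary outcome, for contrast** (2.G, Primary analysis): residual volume before the procedure is a model covariate in its own right.

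**The concern.** A postoperative recovery score partly reflects how the patient slept, felt and functioned before the operation. Without a preoperative score, that part cannot be separated from the noise against which the treatment difference is judged. The imbalance rule in 2.G does not help, because it can act only on variables that are collected. The plan accepts the principle for residual volume but does not carry it over to QoR-15.

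A smaller, related matter concerns ORSDS. For the last 24 hours the form asks "have you experience any of the following", and its 12 items include constipation, fatigue, dry mouth and headache. It does not ask whether the symptom is new. Chronic opioid users are enrolled and form a randomisation stratum, so some patients may bring such symptoms with them.

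At stake is the chance of detecting a real difference on a tested secondary outcome for which the plan states no power.

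**Working it through.** **The plan's own figure.** Section 2.H gives 62 per group for the primary outcome: 90% power, two-sided 0.05, effect size 0.4, four measurements, correlation 0.3. For one measurement, n = 2 × ((1.960 + 1.282)/0.4)² = 131.3 per group. Averaging four equally correlated measurements multiplies this by (1 + 3 × 0.3)/4 = 0.475, so 131.3 × 0.475 = 62.4. Power at 62 is 89.8%. The figure reproduces and is not disputed. It says nothing about QoR-15, which has one measurement, a stricter alpha and no stated power.

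**Inputs for QoR-15.**
- 62 analysed per group (2.H, before the allowance for loss to follow-up).
- Alpha 0.05/3 = 0.0167 two-sided (2.G), critical value 2.394.
- One value per patient, so the planned mixed model reduces to an ordinary linear model.
- Correlation r between preoperative and postoperative QoR-15: not in the documents. Assumed range 0.2 to 0.6.
- A difference of 0.5 SD as reference: also an assumption, since the plan names no target for QoR-15.

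**Formulas.** With baseline as covariate, residual SD = √(1 − r²) in units of the unadjusted SD.
- Power ≈ Φ(0.5/(√(1 − r²) × √(2/62)) − 2.394).
- Detectable difference at 80% power = (2.394 + 0.842) × √(1 − r²) × √(2/62).

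Without baseline: 0.5/√(2/62) = 2.784; 2.784 − 2.394 = 0.390; Φ(0.390) = 65%. The detectable difference is 3.236 × 0.1796 = 0.58 SD.

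| r (assumed) | Fall in residual variance, r² | Power for 0.5 SD | Detectable at 80% power | n per group, 0.5 SD at 80% |
|---|---|---|---|---|
| no baseline | – | 65% | 0.58 SD | 84 |
| 0.2 | 4% | 67% | 0.57 SD | 81 |
| 0.3 | 9% | 70% | 0.55 SD | 77 |
| 0.4 | 16% | 74% | 0.53 SD | 71 |
| 0.5 | 25% | 79% | 0.50 SD | 63 |
| 0.6 | 36% | 86% | 0.47 SD | 54 |

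**ORSDS.** Suppose a share b of patients has a symptom that was present before surgery and persists equally in both arms, and let q be the new-onset rate. The observed rate of any symptom is then b + (1 − b)q, and the risk difference is (1 − b) times the new-onset difference. The documents give neither b nor q, and equal persistence is itself an assumption, so no size is claimed.

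**The case against.** The strongest reply is that nothing here is an error. Allocation is randomised 1:1, blinded and stratified on chronic opioid use. Comparing postoperative scores alone is valid, and chance imbalance in an unmeasured score is already covered by the type I error. The trial is powered for residual volume only. All of this stands. A reader might infer that the missing baseline biases the comparison between arms; the design does not support that.

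The gain also rests wholly on an assumed correlation, and at r = 0.2 it is small. Collected variables such as functionality and chronic pain may explain some of the same variance, though the plan uses them only when they are imbalanced. This stands as a caution about size.

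Three further inferences are tempting and go too far.
- **The form.** The "QoR-15 Patient Survey" in the Appendix has boxes for preoperative and postoperative use. That might suggest a planned baseline that was then left out of the schedule. But the form is reproduced from a cited source, so the box shows only that a baseline can be recorded.
- **Pre-existing symptoms.** A reader might conclude that every preoperative symptom is counted as an opioid side effect. It counts only if it is present in the 24 hours before a POD 1 or POD 2 form.
- **Counting only new or worsened symptoms.** This looks like the natural remedy. But sections 1.C and 1.D of the Introduction describe naloxegol as a treatment for opioid-induced constipation. In chronic users, such a rule could discard relief of symptoms that they already had.

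Part of the weakness of the side-effect endpoint also lies in its any-versus-none definition over 12 symptoms, which a baseline form does not cure.

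**Conclusion.** The point holds as an inexpensive improvement to one secondary outcome. QoR-15 is analysed without a baseline that could be collected at an existing contact. The consequence is lower precision for QoR-15; the primary and catheterisation outcomes are untouched.

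At 62 analysed per group and alpha 0.0167, power for an assumed 0.5 SD difference is 65% as planned. It would be about 67% to 86% with a baseline covariate if r lies between 0.2 and 0.6. Where r falls in that range cannot be settled from the documents.

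For ORSDS the conclusion is weaker. Symptoms that persist from before surgery are included in the event count, and a baseline form could account for some of that variation, but the extent is unknown.

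**What to change.** - **Table 1 and 2.F:** add QoR-15 at the preoperative visit, or on the morning of surgery before the first dose of study drug. It cannot be recovered later.
- **2.G, Secondary and exploratory analysis:** include baseline QoR-15 as a prespecified covariate in the QoR comparison, whether or not it is imbalanced. State in advance how a missing baseline form is handled, so that the patient stays in the analysis.
- **Optional:** collect ORSDS at the same contact and enter it as a prespecified covariate in the side-effect model. Leave the endpoint as presence of symptoms, and do not restrict it to new or worsened ones.

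The cost is a few minutes per patient at a contact that already exists, one covariate per model, and occasional missing baseline forms. Both instruments are already in the Appendix. The sample size need not change.

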## Secondary Aim 3:

To assess whether Naloxegol is associated with improved quality of recovery, as measured by the 15-item Quality of Recovery scale.

Hypothesis: Our hypothesis is that patients who received Naloxegol 25 mg given once in the morning every day will have improved quality of recovery. Quality of recovery in the postoperative period is an important measure of the early postoperative health status of patients, and the 15-item Quality of Recovery scale is a validated and efficient measure[32]. Patients will be questioned on the morning of postoperative day (POD) 2 or day of discharge (whichever comes earlier).

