#### Primary analysis.

We will test the primary hypothesis that subjects who received Naloxegol 25 mg given once in the morning every day will have lower volume of residual urine in bladder when compared to placebo. We will compare the randomized groups on the volume of residual urine in bladder, which will be measured twice per day for up to 3 days (i.e., a maximum of 6 measurement times in total), using a linear mixed model adjusting for the within-subject correlation (using an autoregressive correlation structure). At each measurement time, the average of the measurements will be analyzed. Any imbalanced baseline characteristics and volume of residual urine in bladder prior to the procedure will be included as covariates in the model. If the group-by-time interaction is non-significant (P > 0.20), we will assess the group difference on the volume of residual urine across over all the measurements. In the presence of a group-by-time interaction, the group difference will be assessed separately at each measurement time and a Bonferroni correction will be made for multiple comparisons to maintain the hypothesis-wise 2-sided type I error at 0.05 (the significance criterion will be 0.05 / 6).

Second, we will assess the treatment effect within chronic opioid users and nonusers using the same statistical methods as above. The significance level will be 0.025 for each of the two subgroup analyses (Bonferroni correction).

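### Quality of recovery is measured once per patient, so the autoregressive mixed model reduces to linear regression; the replacement model should always include the chronic-opioid-use stratum.

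*Combined protocol and SAP*

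**What the plan says.** Three places in the current text set the timing of the QoR-15, and all give one value per patient.

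- Secondary Aim 3: "Patients will be questioned on the morning of postoperative day (POD) 2 or day of discharge (whichever comes earlier").
- Section F, Measurements: "quality of recovery on 2 or day of discharge (whichever comes earlier").
- Section G, Secondary and exploratory analysis, names the outcome as the "Quality of Recovery scale measured on POD 2 (or day of discharge if it occurs earlier").

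Table 1 in the Study Overview has a single mark in the row "Quality of recovery survey".

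The sentence in Section G that names this outcome goes on to specify the comparison "using a linear mixed model with an autoregressive correlation structure". QoR is one of three secondary hypotheses, and the two-sided error for "each of the secondary outcome will be controlled at 0.017 (i.e., 0.05/3, Bonferroni correction").

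On covariates, the opening paragraph of Section G adjusts every outcome for any baseline variable whose standardized difference exceeds 0.2 in absolute value, and the secondary analysis paragraph repeats the adjustment for imbalanced characteristics. Section E, Protocol, stratifies the 1:1 randomisation by chronic opioid use. Neither analysis paragraph enters that stratum in the model as a matter of course.

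**The concern.** An autoregressive structure describes how repeated values in one patient are correlated. It suits the primary outcome, residual urine, which is "measured twice per day for up to 3 days (i.e., a maximum of 6 measurement times in total"). It has nothing to work on for an outcome taken once. The summaries of changes for Versions 4 and 5 record that QoR assessment was cut back, so the model may be left over from a repeated-measures plan. The mismatch does not depend on that history, because it lies within one sentence of the current text.

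The covariate rule raises a separate question about the same analysis. Stratification is meant to balance chronic opioid use between groups, and the rule admits only variables that turn out imbalanced. The better stratification works, the less likely the stratum is to enter the model. If chronic opioid users recover differently, the variance they contribute stays in the residual. The model-based standard error is then larger than the stratified design warrants.

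**Working it through.** **Inputs.** QoR values per patient: 1 (Secondary Aim 3, Section F, Section G, Table 1). Alpha per secondary outcome: 0.017 (Section G). Patients per group before the dropout allowance: 62 (Section H). Imbalance threshold: 0.2 (Section G). The documents give no power, SD or expected difference for QoR, so there is no planned QoR figure to reproduce. The alpha does reproduce: 0.05/3 = 0.01667, which rounds to 0.017.

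**Step 1: the correlation term.** For m values per patient, the AR(1) covariance has entries σ²ρ^|i−j|. With m = 1 the only entry is i = j, so the matrix is σ²ρ⁰ = σ² for every ρ. The parameter ρ does not appear in the likelihood. A patient random intercept with variance τ² fares no better: each value has variance τ² + σ², and only the sum can be estimated.

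**Step 2: numerical confirmation.** One value per patient was simulated for 62 per arm, with arbitrary mean 100, group difference 3 and SD 15. This checks the algebra and is not a forecast for this trial.

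| ρ | Log-likelihood | SE of group effect |
|---|---|---|
| 0 | −496.2036 | 2.396 |
| 0.3 | −496.2036 | 2.396 |
| 0.6 | −496.2036 | 2.396 |
| 0.9 | −496.2036 | 2.396 |
| Ordinary least squares | – | 2.396 |

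The likelihood is flat in ρ and the standard error is that of ordinary regression.

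**Step 3: would the 0.2 rule pick up the stratum?** The standardized difference is the difference in proportions divided by the pooled SD. The share of chronic opioid users is not given; assume 10% for illustration. The SD is √(0.10 × 0.90) = 0.30, so the threshold is a difference of 0.2 × 0.30 = 0.06, or 0.06 × 62 = 3.7 patients per group. The groups would have to differ by about 4 chronic users before the stratum entered, which is the imbalance stratification is meant to prevent.

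**Step 4: what inclusion could gain.** With the stratum balanced across groups, confidence interval width scales with √(1 − R²), where R² is the share of QoR variance the stratum explains. The documents do not give R².

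| Assumed R² | √(1 − R²) | CI narrower by |
|---|---|---|
| 0 | 1.000 | 0% |
| 0.8% | 0.996 | 0.4% |
| 5% | 0.975 | 2.5% |
| 10% | 0.949 | 5.1% |

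To relate R² to a QoR difference of d SD between users and non-users, take R² = p(1−p)d² / [1 + p(1−p)d²] with p = 0.10. A difference of 0.3 SD gives 0.0081/1.0081 = 0.8%. Solving for d, R² of 5% needs √(0.05/0.95/0.09) = 0.76 SD and R² of 10% needs √(0.10/0.90/0.09) = 1.1 SD. At that assumed share of users, the upper rows need large differences.

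**The case against.** The strongest reply is that the autoregressive wording does no harm. Step 1 supports it: once the idle term is removed, one model remains, linear regression on group plus the covariates the plan already prescribes, with the same estimate and standard error. A reader might infer that the analysis cannot be fitted, or that the analyst must choose a replacement after seeing data. The documents support neither. Only ρ is inestimable; no failed fit has been shown, and software may return the group estimate with or without a warning. Nor does the alpha allocation to QoR make this an error-rate problem.

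The appendix form has preoperative and postoperative labels, which might suggest a second value. No preoperative QoR is scheduled and the analysis paragraph does not use one, so the form does not rescue the repeated-measures model.

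On the stratum, it is fair to say that the omission is not peculiar to QoR: the same covariate rule governs the primary and other secondary analyses. The primary analysis does examine users and non-users separately, but that does not put the stratum in the overall model. It is also fair that the benefit may be close to zero. Both stand as limits on the size of the point. Neither is a reason to leave a design factor out when the sentence is being rewritten anyway.

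**Conclusion.** The mismatch is real but minor. The autoregressive term is redundant, and removing it changes no estimate, standard error or error rate; the gain is a plan that describes the analysis actually done. The substantive part is the stratum. Leaving it out makes the standard error conservative to the extent that chronic opioid use predicts QoR. A reader might infer a gain of several per cent in interval width, but the documents support no particular figure: the range is about 0 to 5% for an assumed R² of 0 to 10%. This rests on stratification achieving the balance it is meant to achieve (Section E does not describe blocking within strata) and on a prognostic strength that the documents do not report.

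**What to change.** In Section G, Secondary and exploratory analysis, replace the QoR model with wording such as: the single QoR-15 score will be compared between groups by linear regression on randomised group and chronic-opioid-use stratum, the stratum always being included, together with any baseline covariates meeting the prespecified imbalance rule; the adjusted mean difference will be reported with its confidence interval at the 0.017 level (a 98.3% interval, since 1 − 0.017 = 0.983).

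Keeping the imbalance covariates matters, because Section G requires them for all outcomes and a model with group and stratum alone would drop that rule without saying so.

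The cost is one sentence and one residual degree of freedom (122 to 121 with 124 patients and no other covariates). The stratum is already known at randomisation, so data collection and sample size do not change.
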